7.3.2.3 Reporting Adverse Events

All AEs reported or observed during the study will be recorded on the AE page of the eCRF. Information to be collected includes drug treatment, dose, event terminology, date of onset, CTCAE Version 4.0 assessment of severity, relationship to study drug, date of resolution of the event, seriousness, any required treatment or evaluations, and outcome. With the exception of disease progression, AEs resulting from concurrent illnesses, reactions to concurrent illnesses, and reactions to concurrent medications also must be reported. All AEs will be followed to adequate resolution. CTCAE Version 4.0 will be used to grade all AEs. The CTCAE includes 5 grades (1 to 5), with Grade 5 being death.

Any AE that meets SAE criteria ([Section 7.3.2.1](#)) must be reported to the contract research organization (CRO) immediately (i.e., within 24 hours after the time site personnel first learn about the event). The following contact information is to be used for SAE reporting:

Pharmacovigilance Department

7.3.2.4 Assessment of Severity

Adverse events are graded according to CTCAE Version 4.0. For events not included in the CTCAE criteria, the severity of the AE is graded on a scale of 1 to 5 as follows:

1:	Mild; asymptomatic or mild symptoms; clinical or diagnostic observations only; intervention not indicated
2:	Moderate; minimal, local or noninvasive intervention indicated; limiting age-appropriate instrumental ADL ^a
3:	Severe or medically significant but not immediately life-threatening; hospitalization or prolongation of hospitalization indicated; disabling; limiting self-care ADL ^b
4:	Life-threatening consequences; urgent intervention indicated
5:	Death related to adverse event

a Instrumental activities of daily living (ADL) refer to preparing meals, shopping for groceries or clothes, using the telephone, managing money, etc.

b Self-care ADL refer to bathing, dressing and undressing, feeding self, using the toilet, taking medications, and not bedridden.

Changes in the severity of an AE should be documented to allow an assessment of the duration of the event at each level of intensity to be performed. Adverse events characterized as intermittent do not require documentation of onset and duration of each episode.

7.3.2.5 Assessment of Causality

The Investigator's assessment of an AE's relationship to study drug is part of the documentation process, but it is not a factor in determining what is or is not reported in the eCRF.

All AEs, regardless of assessment of causality, are reported in the eCRF.

All SAEs considered at least possibly related to the study drug will be considered unexpected; and therefore, reported as suspected unexpected serious adverse reactions (SUSARs).

7.3.2.6 Follow-Up of Patients Reporting Adverse Events

All AEs must be reported in detail on the appropriate page of the eCRF and followed to satisfactory resolution, until the Investigator deems the event to be chronic or not clinically significant, or until the patient is considered to be stable.

7.3.3 Pregnancy

Any pregnancy that occurs during study participation must be reported using a clinical study Pregnancy Report Form. To ensure patient safety, each pregnancy must be reported as described for reported AEs in [Section 7.3.2.3](#), upon learning of its occurrence. The pregnancy must be followed to determine outcome (including spontaneous miscarriage, elective termination, normal birth, or congenital abnormality) and status of mother and child, even if the patient was discontinued from the study. The outcome of the pregnancy will be reported on the Pregnancy Outcome Form. Spontaneous miscarriages must be reported as an SAE.

Any SAE occurring in association with a pregnancy brought to the Investigator's attention after the patient has completed the study and considered by the Investigator as possibly related to the study treatment must be promptly reported ([Section 7.3.2.3](#)).

7.3.4 Clinical Laboratory Analyses

Samples will be collected at the time points specified in [Appendix 13.1](#).

Any clinically significant abnormal laboratory test results are to be recorded as AEs or SAEs per CTCAE Version 4.0.

7.3.4.1 Hematology

The complete blood count (CBC) includes WBC with 5-part differential, platelet count, hemoglobin, hematocrit, and ANC. Peripheral blasts will be included in the hematology analysis for Part 2 only. If the WBC value is $<400 \times 10^6/L$, a differential is not required. The coagulation panel includes prothrombin time (PT), International Normalized Ratio (INR), and partial thromboplastin time (PTT). Patients taking coumarin-derivative anticoagulants should be monitored closely and their anticoagulant dose adjusted as needed.

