7.3.1 Dose-Limiting Toxicities and Dose-Escalation Scheme

7.3.1.1 Definition of Dose-Limiting Toxicities

A DLT is defined as any of the following events, except those that are clearly due to underlying disease or extraneous causes:

- A hematologic DLT is defined as:
 - Grade 3 or higher event of neutropenia and/or thrombocytopenia or a Grade 4 anemia, with a hypocellular bone marrow lasting for 6 weeks or more after the start of a cycle, in the absence of residual leukemia (i.e., with <5% blasts). In case of a normocellular bone marrow with <5% blasts, 8 weeks with \geq Grade 3 pancytopenia will be considered a DLT.
- A non-hematologic DLT is defined as:
 - Grade 4 tumor lysis syndrome (Grade 3 TLS will not constitute DLT unless it leads to irreversible end-organ damage).
 - Grade 3 or higher AEs (including nausea, vomiting, diarrhea, and electrolyte imbalances lasting more than 48 hours despite optimal therapy; excluding all grades of alopecia).
 - Grade 3 or higher hypersensitivity reaction (regardless of premedication).
 - Grade 3 or higher skin ulceration.
 - Peripheral sensory or motor neuropathy \geq Grade 2.

Note: The DLT observation period for dose-escalation will be 1 cycle. Patients who experience a DLT during Cycle 1 are to be permanently discontinued from the study.

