3.3 Modifications to the statistical section of the protocol

The trial was terminated early, prior to the completion of dose escalation (part 1), therefore, only Part 1 data has been analyzed and a selected or modified analysis from the statistical section of the protocol will be performed. Please see details in each section.

4 Statistical methods

All analyses use SAS® version 9.4 or higher. Summary tables will be organized by each dose level; if some dose levels have only a few subjects, then dose levels can be combined into dose ranges. All available data will be used in the analyses, and important data will be included in data listings, sorted by dose level, subject, and by visit within subject. Missing data will not be imputed, except via censoring in survival analyses and as otherwise specified.

Unless otherwise noted, categorical data will be presented using counts and percentages, with the number of subjects in the analysis set by treatment group as the denominator for percentages. Percentages will be rounded to one decimal place, except 100% will be displayed without any decimal places, and percentages will not be displayed for zero counts. Continuous data, unless otherwise noted, will be summarized using the number of observations (n), mean, standard deviation (std), median, minimum, and maximum. Minima and maxima will be rounded to the precision of the original value, and means, medians, and confidence intervals (CIs) if presented will be rounded to 1 decimal place greater than the precision of the original value. The std will be rounded to 2 decimal places greater than the precision of the original value, up to a maximum of 3 decimal places.

No hypothesis testing will be performed in this study.

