4.8.1 Laboratory Data

Descriptive statistics (mean, standard deviation, median, and range) will be calculated for the raw data and for their changes from baseline at each scheduled assessment.

All results will be summarized using shift from baseline. Shifts for clinical laboratory results that can be graded according to CTCAE version 4.0 will be summarized by CTCAE grade.

Summaries by visit will include data from scheduled assessments, and all data will be reported according to the nominal visit date for which it was recorded. Unscheduled data will be included in “worst case post baseline” summaries, which will capture a worst case across all scheduled and unscheduled visits after the first dose of study treatment.

Laboratory data, including urinalysis, will be listed. Pregnancy test results will not be listed, but will be included in datasets.

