6.1 General conventions

6.1.1 Missing data

Handling of missing relationship to investigational product of AEs

If the assessment of the relationship to investigational product is missing, then the relationship to investigational product has to be assumed and the AE considered as such in the frequency tables of possibly related AEs, but no imputation should be done at the data level.

Handling of missing severity/grades of AEs

If the severity/grade is missing for one of the treatment emergent occurrences of an AE, the maximal severity of the remaining occurrences will be considered. If the severity is missing for all the occurrences a “missing” category will be added in summary table.

No other imputation of values for missing data will be performed.

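### Below a WBC of 0.4 x10^9/L the differential may be skipped and the SAP has no rule for the gap, so the neutrophil and lymphocyte laboratory tables can lean toward milder cytopenia

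*Protocol*

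**What the plan says.** Protocol 7.3.4.1 defines the complete blood count as "WBC with 5-part differential, platelet count, hemoglobin, hematocrit, and ANC". It then makes an exception for a WBC below 400 x10^6/L, where "a differential is not required". The exception names the differential only. It neither waives ANC nor says how ANC would be obtained without a differential.

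The SAP sets its general rule in section 4: "Missing data will not be imputed, except via censoring in survival analyses and as otherwise specified". Section 6.1.1 gives two conventions, both for adverse events (missing relationship and missing grade), and closes with: "No other imputation of values for missing data will be performed".

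The SAP's Laboratory Data section plans three kinds of output:

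- descriptive statistics and change from baseline by visit;
- shifts from baseline: "Shifts for clinical laboratory results that can be graded according to CTCAE version 4.0 will be summarized by CTCAE grade";
- a worst-case post-baseline summary, "which will capture a worst case across all scheduled and unscheduled visits after the first dose of study treatment".

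Baseline is the last non-missing value up to first dose (SAP 4.8). SAP 6.1.2 and 6.1.3 cover unscheduled and duplicate visits. None of these sections addresses a sample with a WBC but no differential.

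**The concern.** Whether a neutrophil count exists can depend on how low the count is. Missingness of that kind is informative, and here its direction is known: every value lost to the waiver is very low. A table built only on measured ANC leaves those samples out, so its grades look milder and its averages higher than the data in hand would justify. The lymphocyte tables are exposed in the same way.

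Safety is a primary endpoint (Protocol 8.2.1), and the agent is a cytotoxic conjugate given to patients with relapsed or refractory leukemia. Protocol 6.4 has patients receive the first two cycles whatever their blood count recovery, so very low WBC is foreseeable. After early termination the SAP only lists efficacy data and DLTs, which leaves the safety tables as a large part of what is summarized.

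**Working it through.** The plan gives no figure to reproduce on this point. The check is a bound, a reading of the rules, and an illustration of size.

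**Step 1: the bound.** 400 x10^6/L ÷ 1000 = 0.4 x10^9/L. ANC = WBC × neutrophil fraction, and the fraction lies between 0 and 1, so WBC <0.4 gives ANC <0.4. With fractions of 25%, 50% and 100% the limits are <0.1, <0.2 and <0.4. The same bound holds for lymphocytes. The documents themselves use ANC levels of 1.0 (response criteria, Protocol 7.1) and 0.5 (count recovery, Protocol 6.4), and 0.4 is below both. The CTCAE cut-offs are not printed in the documents. I assume Grade 4 neutropenia is ANC <0.5, and any cut-off of 0.4 or more classifies these samples in the same way.

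**Step 2: what the SAP does with such a sample.** The SAP allows only survival censoring and the two AE conventions as exceptions, and gives no laboratory rule. A sample without ANC therefore has no neutrophil grade and enters none of the three laboratory outputs for ANC.

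**Step 3: size, on assumed inputs.** Log WBC = log(median) + patient effect (SD 0.9) + sample effect (SD 0.6). The neutrophil fraction is Beta(2,4), with mean 2/(2+4) = 1/3. There are four post-dose samples per patient and 200,000 simulated patients, and every waived differential is skipped. The share of samples below 0.4 is Φ[(ln 0.4 − ln median)/√(0.9² + 0.6²)], where the root is 1.08.

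| Median WBC (x10^9/L) | Samples losing ANC | Patients with worst ANC <0.5: true → tabulated | Median ANC: true → tabulated |
|---|---|---|---|
| 0.5 | 42% | 98% → 77% | 0.14 → 0.28 |
| 1.0 | 20% | 91% → 84% | 0.29 → 0.39 |
| 2.0 | 7% | 77% → 75% | not tabulated here |

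At median WBC 0.5, 20% of patients have no post-dose ANC at all.

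**Step 4: sensitivity.**

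- *Number of samples.* Two Q3W cycles give about six post-dose hematology samples (Cycle 1 Days 8 and 19; Cycle 2 Days 1, 8 and 19; End of Treatment). At median WBC 1.0 the worst-case loss is then about 5 points, and with eight samples it is 96% → 93%. A patient leaves the worst-case count only if every qualifying sample was waived. If 30% are waived independently, the chance is 0.3 for one such sample, 0.3² = 9% for two and 0.3³ = 2.7% for three.
- *Share actually skipped.* If a random half of waived differentials are skipped, the worst-case loss at median WBC 1.0 with four samples is under 1 point. The by-visit statistics remain biased.
- *Neutrophil fraction.* With a mean of one half, the change at median WBC 1.0 is 82% → 73%.

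**Step 5: would substituting the bound repair the median?** At median WBC 0.5 the true median ANC is 0.14. Dropping the records gives 0.28, inserting the recorded WBC gives 0.24, and inserting a fixed 0.4 gives 0.40. Inserting WBC leaves (0.24 − 0.14)/(0.28 − 0.14) = 71% of the bias, and a fixed 0.4 is worse than dropping. The bound is sound for grades but not as a substituted value.

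**Step 6: baseline.** Inclusion criterion 9 sets only an upper limit on WBC, so a pre-dose sample below 0.4 is possible. If its ANC is missing, the last-non-missing rule takes an earlier ANC. Where that value is higher, the shift is overstated, so this part of the bias can run the other way.

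**The case against.** The strongest reply is that the documents show only that ANC may be missing. The waiver is permissive, ANC remains a listed item of the blood count, and nothing says how often a count was absent. That stands, and it is why the figures above are illustrations and not estimates.

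A second reply is that grading from a recorded WBC is a logical derivation and not imputation, so the SAP does not forbid it. That is fair as far as it goes: the fault is a missing rule, not a wrong one. But with imputation closed off in general terms and no derivation described, the default is to leave the grade blank.

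A reader might infer two stronger things. One is that the trial under-counts severe neutropenia overall. The documents do not support this. Protocol 7.3.4 requires clinically significant laboratory abnormalities to be recorded as graded AEs, the SAP tabulates TEAEs by maximum grade, and total WBC stays in the laboratory tables. Nor are the lost values necessarily the lowest: a sample with a higher WBC made up mostly of blasts can have a lower ANC.

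The other is that DLT assessment is compromised. The hematologic DLT does start from "Grade 3 or higher event of neutropenia and/or thrombocytopenia", but it also needs marrow findings and six or eight weeks' duration. The Dose-Escalation Steering Committee determines DLTs and the SAP only lists them, so the SAP's missing-data rule does not govern that decision.

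**Conclusion.** The gap is real and limited to the ANC and lymphocyte laboratory outputs. Any post-baseline record lost through the waiver is provably below 0.4 x10^9/L, so leaving it out moves those shift, worst-case and by-visit results toward milder cytopenia. A waived baseline sample can act in the opposite direction.

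The size depends on WBC levels, the number of samples and how many differentials were really skipped, and the documents give none of these as data. On the assumptions shown, with all waived differentials skipped, the worst-case loss runs from about 2 points (median WBC 2.0, four samples) to about 21 points (median WBC 0.5, four samples). Nothing in the documents marks the latter as typical. If no ANC is missing, the effect is nil. The study is descriptive, with no hypothesis tests, so no test result is at risk. The rule is still worth adding, because the severity of these records can be shown from a value already in the database.

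**What to change.** Add a rule to the SAP's Laboratory Data section and name it as an exception in 6.1.1:

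- **Grades.** When WBC is below 0.4 x10^9/L and no differential or ANC is reported, derive the neutrophil grade and the minimum lymphocyte grade using the recorded WBC as upper bound. Leave any reported ANC or lymphocyte count as it is.
- **Scope.** Apply the rule to baseline and post-baseline records alike in the shift and worst-case tables. Flag derived grades in the listings.
- **By-visit statistics.** Report the number of such records at each visit and treat them as left-censored at the recorded WBC. Do not enter the bound as if it were a measurement. For example, give the median as '< x' when it falls among these records, and label means as based on measured values only.

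The cost is a small programming step on data already collected. The neutropenia rates in the laboratory tables may become slightly less favourable. If no counts turn out to be missing, the tables do not change.

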7.3.4.2 Biochemistry

Tests for clinical biochemistry include ALT, AST, gamma-glutamyl transferase, alkaline phosphatase, amylase, lipase, total bilirubin, sodium, potassium, calcium, magnesium, blood urea nitrogen or urea, carbon dioxide/bicarbonate, chloride, creatinine, creatine phosphokinase, total protein, albumin, glucose, triglycerides, total cholesterol, phosphorus, and lactate dehydrogenase. Biochemistry will include creatinine clearance⁹..

7.3.4.3 Urinalysis

Urinalysis will include pH, specific gravity, protein, occult blood, glucose, ketones, nitrites and bilirubin. The urinalysis may be performed using a urine dipstick.

7.3.4.4 Additional Renal Function Studies

Urine will be collected for testing of biomarkers suggestive of potential renal injury (aquaporin-2, calbindin D28, and clusterin). Analysis of this additional urine sample will be performed at a central laboratory (instructions provided in the Laboratory Manual).

7.3.4.5 Additional Microbiological Serological studies

Patients will be regularly examined and asked whether they have been suffering from an infection during their participation in the trial. If there is a reasonable suspicion that such infection could have been caused by one of the pathogens listed below, appropriate microbiological workup must be conducted. Should such workup indicate that infection was indeed caused by one of those microorganisms, re-dosing must be delayed so that there is at least a four-week window between symptom resolution and the next dose of ADCT-301.

Pathogens of interest are: HSV1, HSV2, VZV, EBV, CMV, measles, Influenza A, Zika virus, Chikungunya virus, mycoplasma pneumonia, Campylobacter jejuni, and enterovirus D68.

7.3.5 Electrocardiograms

On Day 1 of Cycles 1 and 2, a 12-lead ECG is to be performed before the start of the ADCT-301 infusion, within 30 minutes of the end of infusion, and 3 (± 30 minutes) and 24 (± 2.4) hours after the end of infusion. On Day 1 of Cycle 3 and subsequent cycles, a 12-lead ECG is to be performed before the start of ADCT-301 infusion.

Any abnormalities, including those that worsen from baseline, believed to be clinically significant in the medical and scientific judgment of the Investigator are to be recorded as AEs or SAEs.

Measurement of the QTc interval may be obtained according to the formula used by the institution; however, the Fridericia formula is preferred.¹² The same formula used to confirm eligibility must be applied within a patient for the duration of the study.

7.3.6 Physical Examination

Physical examinations will include a complete review of body systems, including whole-body skin assessment. Whole-body skin assessment does not have to be performed by a dermatologist. However, any unexplained lesion is to be referred to a dermatologist for further evaluation and biopsy if clinically warranted. Physical examination will also include a neurological examination of strength, sensation, and deep tendon reflexes; unexpected findings will be referred to a neurologist for further evaluation. Height will be measured at the Screening Visit (Day -28 to -1) and weight will be assessed before treatment as follows:

Every 3-Week Schedule: Day 1 of each cycle, Days 8 and 19 of Cycles 1 and 2, and at the EOT Visit.

Weekly Schedule: Days 1, 8, 15 of each cycle and at the EOT Visit.

The examination must include a determination if the patient has had any infection. At the discretion of the investigator, evaluation of any reported infection must be conducted to rule out infection with a microorganism that may be associated with autoimmune or neurological disease(s) as specified in the exclusion criteria.

Any clinically significant abnormalities, including those that worsen from baseline, are to be recorded as AEs or SAEs.

7.3.7 Vital Sign Measurements

Vital signs measurements will include arterial blood pressure, heart rate, respiratory rate, and temperature. Any clinically significant abnormalities, including those that worsen from baseline, are to be recorded as AEs or SAEs.

7.3.8 Eastern Cooperative Oncology Group Performance Status

The patient's performance status will be assessed according to the time points in the schedule of events ([Appendix 13.1](#)) using the ECOG performance status grades below:²⁶

0:	Fully active, able to carry on all predisease performance without restriction
1:	Restricted in physically strenuous activity but ambulatory and able to carry out work of a light or sedentary nature, e.g., light house work, office work
2:	Ambulatory and capable of all self-care but unable to carry out any work activities. Up and about more than 50% of waking hours
3:	Capable of only limited self-care, confined to bed or chair more than 50% of waking hours
4:	Completely disabled. Cannot carry on any self-care. Totally confined to bed or chair
5:	Dead

7.4 Sample Handling, Storage and Shipment

Detailed instructions for central laboratory sample collection, labeling, processing, storage, and shipping will be provided to the site in the Laboratory Manual.

During the study, whole blood samples will be collected for PK, ADA, cytokines, CD25 expression, PD (soluble CD25 [sCD25], analysis of peripheral WBC populations), CD34 expression (and other CD markers), and safety analyses (clinical chemistry, cytokine and hematology). MNCs isolated from BMA and MNCs isolated from whole blood samples will be collected for screening and disease assessment.

For PK, ADA, cytokines, sCD25 and cytokine, whole blood samples are to be collected and processed on site. The resulting serum samples should be aliquoted and stored until shipment. Each sample must be clearly labeled with the following information: study number, study center number, patient number, tube identification, and the sample collection time point (by day and hour), when necessary.

The central laboratory samples are to be packed in sufficient dry ice and shipped from the study center to the central laboratory. Where possible, samples should be stored at -70°C or below. Samples should be shipped according to the sample shipment schedule provided in Laboratory Manual. [REDACTED]

Clinical chemistry and hematology samples, which should not be frozen, are to be transferred at ambient temperature to local laboratories.

For the analysis of peripheral WBC populations, whole blood is to be collected and shipped, as per the Central Laboratory Manual, directly to the testing central laboratory for immediate processing.

Bone marrow samples and whole blood samples for Screening and disease assessment are to be taken and processed on site according to local clinical procedures. At Screening, any remaining sample material is then to be processed and frozen according to the Laboratory Manual. The resulting MNC cell preparation should be transferred as frozen samples (-70°C or below) to the testing central laboratory.

8 Statistical and Analytical Plan

Full details of the analysis plan, including a more technical and detailed elaboration of the statistical analyses will be provided in the statistical analysis plan (SAP).

